**4.4.3. Specific Withdrawal Criteria and Replacement Procedure for Phase 2a**

- Patients who do not have at least 1 post baseline assessment for efficacy will be withdrawn from the study and may be replaced.
- Patients who are found to have protocol violations that substantially impair the evaluation of safety and efficacy may be replaced.

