#### 11.1.1. Analysis Populations

The safety analysis population will consist of all patients treated with at least 1 dose of study medication (cerdulatinib). Safety data will be summarized by dose level, based on the original assigned dose of study drug.

The efficacy analysis population for the primary and secondary efficacy endpoints will consist of all patients who have taken at least 1 dose of study medication and have had at least 1 post-baseline tumor assessment. Efficacy will be summarized separately for Phase 1 and 2a, and within Phase 2a, efficacy will be summarized by cohort and dose level.

The PK and PD analysis populations will consist of all patients who have received the requisite treatments and have data at the required time points. Any windows for timing of measurements, etc., will be specified in the SAP.

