## **11.3. Missing Data**

No imputation of missing data will be performed. Patients who do not have sufficient information for evaluation of response will be listed with the reason for missing response, and the count will be summarized.

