- Vital signs include temperature, respiration, blood pressure and heart rate, and should be obtained after at least 5 minutes in the sitting or semi-recumbent position. Post-dose vital signs should be obtained at 1.0 hour post-cerdulatinib administration for all patients except those in Cohort 2 for all onsite visits. For patients in Cohort 2 (cerdulatinib + rituximab), on visits when rituximab is administered, post-dose vital signs should be obtained at 0.5, 1.0, 2.0, 3.0, and 4.0 hours post-cerdulatinib dosing (or per standard of care), and then as clinically indicated. The collection window for vital signs is ± 10 minutes.
- Administer Global Health Assessment before any other protocol procedures are performed and before any protocol-related information is communicated.
- Record all medications including over the counter preparations, herbals, and vitamins taken in the 14 days prior to Cycle 1 Day 1.
- Dosing begins on Day 1 and continues daily until treatment interruption or study discontinuation.
- Rituximab dose is 375 mg/m^2. Rituximab infusion should start immediately after cerdulatinib is taken.
- After Cycle 1, rituximab should be administered on Day 1 only of Cycles 4, 6, 8, and 10.
- For CLL patients only, a bone marrow biopsy and aspiration will be completed before Day 1 (within 6 weeks/42 days prior to Day 1) through the local lab and be repeated as clinically indicated. For all other patients with a history of bone marrow involvement prior to entering the study, a repeat biopsy should be performed to confirm a complete response or as clinically indicated.
- CT or CT/PET of chest, abdomen, pelvis, and any other areas of lymphoma may be obtained within 28 days prior to Cycle 1 Day 1; redacted copy of the report(s) to be available to the Sponsor for review. Subsequent CT or CT/PET assessments may be performed within 7 days prior to the scheduled visit and as clinically indicated. For CTCL patients, if baseline scan is negative for nodal/visceral/other disease, a repeat CT or CT/PET is not necessary except to confirm CR and may be done as clinically indicated. In the event of a Complete Response, confirmatory scans should be obtained no less than 4 weeks following determination of response. Copies of scans should be made available to Sponsor upon request. Additionally, obtain copy of molecular/mutation profile if obtained as standard of care.

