6. ANALYSIS POPULATIONS

The safety analysis population will consist of all patients treated with at least 1 dose of study medication (cerdulatinib or rituximab). The safety analysis population will be used for all safety analyses. Subjects disposition, demographics, baseline characteristics, and treatment exposure will also be analyzed based on the safety analysis population.

The efficacy analysis population will consist of all patients who have taken at least 1 dose of study medication and have had at least 1 post-baseline investigator response assessment (IRA). The efficacy analysis population will be used for the primary and secondary efficacy endpoints for the follicular lymphoma (FL) patients in Cohort 1 and 2 and the peripheral T-cell lymphoma (PTCL) patients in Cohort 5. In addition, efficacy will also be assessed in the corresponding safety analysis population in Cohort 1, 2, and 5.

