7.2. Subject Disposition

The following subject disposition information will be summarized:

- Number of subjects treated
- Number and percentage of treated subjects who discontinued treatment
- Primary reason for treatment discontinuation

The number of subjects treated will be summarized by site. Due to inconsistencies in different versions of protocol and data entry instructions in study follow-up, the number of subjects who discontinued study will not be summarized.

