7.8. Efficacy analysis

The efficacy of the Phase 1 patients will be presented in the subject listing only. For Phase 2a patients, efficacy will be summarized and analyzed for the FL patients in Cohort 1 and 2 and the PTCL patients in Cohort 5 only. For FL subjects in Cohort 1 and 2, efficacy will be summarized by number of prior regimens (≤ 3 vs ≥ 4). Efficacy of PTCL will be summarized by pathology subgroup as defined in Appendix B (AITL/TFH vs NOS vs Others). The efficacy listing will be provided for non-FL/non-PTCL patients in Cohort 1, 3, 4, and 6.

All efficacy analyses will be based on the efficacy analysis population. The efficacy analyses will also be analyzed in the corresponding safety analysis population in Phase 2a Cohort 1, 2, and 5 as sensitivity analyses.

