7.8.2. Secondary Efficacy Endpoint

7.8.2.1. Progression free survival

Progression-free survival (PFS) is defined as the time from the start of study treatment to the first documentation of disease progression as assessed by investigator (see appendix C) or death from any cause, whichever occurs first.

Progression-free survival = (first documentation of disease progression or death – first dose date of study treatment + 1) /30.4375 in months.

PFS will be right censored for subjects who meet one of the following conditions: 1) no baseline disease assessments; 2) starting a new anti-cancer therapy before documented disease progression or death; 3) progression or death immediately after more than 6 months since the last disease assessment (or more than 12 months if beyond cycle 12); and alive without documented disease progression. The censoring convention follows the FDA guidance for Industry Clinical Trial Endpoints for the Approval of Cancer Drugs and Biologics (2018) and references within the guidance document. The censoring rules are summarized in Table 1.

Table 1. Date of Event or Censoring for PFS

Scenario	Date of PFS Event or Censoring	Outcome
Death or progression between the planned disease assessments	Date of death or first disease assessment showing PD, whichever occurs first	Event
Death before the first disease assessment	Date of death	Event
No baseline disease assessment	Date of first dose of study treatment	Censored
New anti-cancer treatment started	Date of last disease assessment prior to or on the date of new anti-cancer treatment	Censored
Death or progression immediately after missing more than 1 scheduled disease assessment ^[1]	Date of the last disease assessment before death or progression	Censored
Alive without documented disease progression	Date of last disease assessment	Censored

^[1] missing ≥ 6 months if in Cycle 1~12 or missing ≥ 12 months if beyond Cycle 12

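### The lead ORR, CBR, dominant mass response and PFS analyses drop treated patients who never had a post-baseline response assessment; the all-treated analysis is only a sensitivity analysis

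*SAP*

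**What the plan says.** SAP Section 6 limits the efficacy analysis population to "all patients who have taken at least 1 dose of study medication and have had at least 1 post-baseline investigator response assessment (IRA") and assigns it to the primary and secondary efficacy endpoints for FL in Cohorts 1 and 2 and PTCL in Cohort 5. This follows Protocol 11.1.1: "all patients who have taken at least 1 dose of study medication and have had at least 1 post-baseline tumor assessment".

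SAP 7.8 bases all efficacy analyses on that set and then adds: "The efficacy analyses will also be analyzed in the corresponding safety analysis population in Phase 2a Cohort 1, 2, and 5 as sensitivity analyses". CBR (7.8.2.4) and dominant mass response (7.8.2.5) are analysed in the same way as ORR, so they share its denominator.

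Protocol 4.4.3 says of patients without an assessment: "Patients who do not have at least 1 post baseline assessment for efficacy will be withdrawn from the study and may be replaced". Cohort expansion is planned in evaluable patients, 40 to 50 per cohort (SAP 5.2).

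On reporting, Protocol 11.3 says patients with insufficient response information "will be listed with the reason for missing response, and the count will be summarized", and SAP 7.1.2 lists the reasons for Cohorts 1, 2 and 5. SAP 7.2 summarizes treatment discontinuation with its primary reason, but states that "the number of subjects who discontinued study will not be summarized".

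For PFS, Table 1 in SAP 7.8.2.1 has the row "Death before the first disease assessment", scored as an event on the date of death.

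**The concern.** Membership of the lead set depends on something that happens after dosing. Scans are planned at screening and then from Cycle 3 Day 1 (Protocol Appendix 1), about 8 weeks after the first dose. Early failures can be lost in that window. Protocol 3.1.2.2.1 reports two fatal infections among the first 12 Phase 2a patients, although it does not give their timing relative to a scan. Not every early failure is lost, because the CT footnote in Appendix 1 allows earlier imaging: "Subsequent CT or CT/PET assessments may be performed within 7 days prior to the scheduled visit and as clinically indicated". Progression recorded at an unscheduled assessment keeps the patient in.

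A single-arm study has no comparator in which the exclusion could cancel. It moves ORR, CBR and dominant mass response in one direction, upward. Replacement can then refill the evaluable number, and a reader of the lead result cannot see how many patients were replaced to reach it.

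The plan also works against its own PFS rule. For a patient who dies with no response assessment, the early-death row of Table 1 can take effect only in the sensitivity analysis.

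**Working it through.** **Inputs.** Planning cases of 30% and 20% observed in 40 patients (Protocol Synopsis, Sample Size Considerations); Clopper-Pearson 95% intervals (SAP 7.8.1); 28-day cycles, so Cycle 3 Day 1 falls 56 days after the first dose; 30.4375 days per month (SAP 7.8.2.1). The unassessed share d is not in the documents and is assumed.

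**The plan's own figures.** 12/40 gives 30.0% (16.6 to 46.5) and 8/40 gives 20.0% (9.05 to 35.65), in agreement with the Synopsis intervals of 16.6% to 46.5% and 9.1% to 35.7%. The upper bound for 1/20 is 24.9%, which the plan rounds to about 25%.

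**ORR.** Let x be the responders, n the evaluable patients and m the treated patients never assessed. All x responders are among the n, so

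- lead ORR = x/n
- all-treated ORR = x/(n + m)
- d = m/(n + m), hence lead ORR = all-treated ORR/(1 − d)

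| Lead ORR | m | d | All-treated ORR (exact 95% CI) | Difference, points |
|---|---|---|---|---|
| 12/40 = 30.0% | 2 | 2/42 = 4.8% | 12/42 = 28.6% (15.7 to 44.6) | 1.4 |
| 12/40 = 30.0% | 3 | 3/43 = 7.0% | 12/43 = 27.9% (15.3 to 43.7) | 2.1 |
| 12/40 = 30.0% | 10 | 10/50 = 20% | 12/50 = 24.0% (13.1 to 38.2) | 6.0 |
| 8/40 = 20.0% | 2 | 2/42 = 4.8% | 8/42 = 19.0% (8.6 to 34.1) | 1.0 |
| 8/40 = 20.0% | 10 | 10/50 = 20% | 8/50 = 16.0% (7.2 to 29.1) | 4.0 |

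Check: 24.0%/(1 − 0.20) = 30.0%. The same factor applies to CBR and dominant mass response, since an unassessed patient cannot be shown to have stable disease or shrinkage. DOR and TTR use responders only and are unaffected.

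**PFS.** Assume exponential times with true median M, so λ = ln 2/M, and that a share q of events before 56/30.4375 = 1.84 months occur with no assessment. Then

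- d = q × (1 − exp(−1.84λ))
- S_lead(t) = exp(−λt)/(1 − d) for t > 1.84
- lead median = M − ln(1 − d)/λ

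| True median | q | d | Lead median |
|---|---|---|---|
| 4 months | 0.10 / 0.25 / 0.50 | 2.7% / 6.8% / 13.6% | 4.16 / 4.41 / 4.85 |
| 6 months | 0.10 / 0.25 / 0.50 | 1.9% / 4.8% / 9.6% | 6.17 / 6.42 / 6.87 |

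Excluded patients who left alive and progression-free would be censored near the start, so leaving them out changes PFS little.

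**The case against.** The strongest reply is that both analyses are already planned for every cohort with aggregated efficacy, so only the label is in dispute. There is no hypothesis test, Protocol 11.1.3 sets no success criterion, and the closure rule counts responses in the first 20 patients without citing the efficacy population. That is correct. No error rate is affected, and it limits the seriousness. It does not change which figure is presented as the study's ORR.

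Much of the reporting also exists. The number excluded is treated N minus efficacy N, missing responses are counted, and reasons are listed. What remains missing is the number replaced and any summary of study discontinuation, although withdrawal from the study is how Protocol 4.4.3 removes these patients.

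Exclusion may also be uncommon. SAP Section 6 asks for an investigator response assessment, not a scan, and the visit 30 days after last treatment includes response assessments (Protocol 7.3.2.2), to be done at discontinuation whenever possible (Protocol 4.4). This bears on d, not on the direction. At d near 5% the ORR shift is 1.0 to 1.4 points, small beside an interval about 30 points wide (16.6 to 46.5). But interval width describes sampling error, and a shift that always has the same sign is a separate matter.

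Two further points stand as caveats. A patient dosed shortly before the data cutoff would be scored a non-responder in the all-treated set without having had the chance to respond; the reasons for exclusion would show such cases. And changing a protocol-specified set late in an open-label study needs justification. Here the change can only lower the headline or leave it unchanged, which makes it easier to defend.

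**Conclusion.** The concern holds and should be fixed. Measured against all treated patients, the lead ORR, CBR and dominant mass response are too high whenever a treated patient goes unassessed and has no recorded response, and they can never be too low. With an assumed 5% to 20% unassessed, the ORR overstatement in the plan's own 40-patient cases is about 1 to 6 points. Under exponential times and assumed true medians of 4 or 6 months, median PFS is overstated by about 0.2 to 0.9 months when 10% to 50% of events before week 8 occur unassessed. The direction for ORR follows from the definitions. Its size depends entirely on d, and the PFS effect depends on why patients went unassessed; the documents give neither. Because the all-treated analysis is already planned, no information is lost. The defect lies in which result leads and in the missing count of replacements.

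**What to change.** - **SAP 6 and 7.8:** make all treated patients in Cohorts 1, 2 and 5 the lead set for ORR, CBR, dominant mass response and PFS, with the evaluable set as the sensitivity analysis. Keep replaced patients who were dosed in the all-treated denominator.
- **Explicit scoring:** state that patients with no assessment count as non-responders, and that early deaths are PFS events under Table 1. At present SAP 7.1.2 only implies the first, through its general rule that missing values stay in the denominator.
- **SAP 7.2:** add, by cohort, the number excluded from the evaluable set and the number replaced, with reasons.
- **SAP 8:** record and justify the departure from Protocol 11.1.1.

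The cost is wording, a few disposition rows and one SAP 8 entry. No new data or programs are needed beyond the added counts, because two planned analyses swap roles. The price is a headline ORR that may be a few points lower, and the need to defend a late change of lead set in an open-label study.

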7. STATISTICAL METHODS

7.1 Data Analysis General Considerations

Where applicable, descriptive statistics will be provided. For continuous variables, n, mean, standard deviation (SD), median, minimum, and maximum will be presented. For discrete variables, the frequency and percentage will be presented. For time to event variables, unless specified otherwise, the Kaplan-Meier (KM) estimate and corresponding two-sided 95% confidence intervals (CIs) will be presented for the median and quartiles and, as necessary, for the event-free rates at the selected time points.

All calculations and analyses will be performed using SAS version 9.4 or higher.

Unless specified otherwise, the Phase 1 portion will be summarized by the initial assigned dose level and the Phase 2a portion will be presented by cancer type. Summaries and analyses will be done for Phase 1 and Phase 2a separately. There will be no pooling of Phase 1 and Phase 2a data. For the subjects enrolled in Phase 1 but continued in Phase 2a, only baseline information (baseline demography, disease characteristics, and prior anti-cancer therapies) from Phase 1 database will be used for corresponding Phase 2a summary tables, all other data will remain separate in Phase 1 and Phase 2a summary tables unless specified otherwise.

7.1.1. Definitions and Computations

Study treatment (study drug): cerdulatinib or rituximab

Study day: study day will be calculated relative to the date of the first dose of study treatment.

Treatment duration: date of last dose of study treatment – date of first dose of study treatment +1

Baseline: unless otherwise specified, a baseline value is defined as the last non-missing value collected on or before the first dose of study treatment (i.e. on/before Cycle 1 Day 1)

7.1.2. Handling of Missing Data

Missing data will not be imputed unless otherwise specified. Missing dates or partially missing dates will be imputed conservatively for adverse events and prior/concomitant medications/procedures as provided in Appendix A.

When summarizing discrete variables, subjects with missing data are generally included in the denominator to calculate percentage unless otherwise specified. In general, a category of “Missing” will be created and the subjects with missing data will be presented.

When summarizing continuous variables, subjects with missing data are not included in calculations unless otherwise specified.

No imputation of AE grades will be performed. AEs with missing CTCAE grades will only be summarized in the all-grade column. If the assessment of the relationship of an AE to study treatment is missing, the AE is assumed to be related to the study treatment in the summary tables. No imputation will be done in the AE listings.

The reason for lack of sufficient information for response evaluation for FL and PTCL subjects in Cohorts 1, 2, and 5 will be listed with reasons for end of treatment/study, death, and any subsequent anti-cancer therapy if applicable.

7.2. Subject Disposition

The following subject disposition information will be summarized:

- Number of subjects treated
- Number and percentage of treated subjects who discontinued treatment
- Primary reason for treatment discontinuation

The number of subjects treated will be summarized by site. Due to inconsistencies in different versions of protocol and data entry instructions in study follow-up, the number of subjects who discontinued study will not be summarized.

7.3. Protocol Deviations

Protocol deviation criteria, types, and classification designations (major vs minor protocol deviations) are defined in the protocol deviation management plan. Protocol deviations are documented and reviewed throughout the study in accordance to the protocol deviation management plan. The list of protocol deviations and their classifications will be finalized prior to the database lock. Final major protocol deviations will be summarized by type and all protocol deviations (both major and minor) will be listed.

7.4. Demographics and other baseline characteristics

If applicable, the following demographic and baseline characteristics will be summarized for Phase 1 portion and Phase 2a portion, respectively.

- Age (years)
- Age group (≤ 65 vs > 65 but ≤ 75 vs > 75)
- Sex
- Ethnicity
- Race
- Weight
- ECG overall result
- ECOG performance status
- Hemoglobin
- Absolute neutrophil count
- Platelet count
- IgG level

- Amylase
- Lipase
- Lymphocyte count
- AST
- ALT
- Creatinine Clearance

In addition, the following disease history and characteristics will be summarized for the follicular lymphoma (FL) patients in Cohort 1 and 2 only.

- Time since initial diagnosis (month)
- Time since the most recent progression (month)
- Baseline bone marrow involvement (Yes vs No)
- Relapsed vs refractory
- Bulky disease (any target lesion with ≥ 7 cm in the longest diameter or at least 3 target lesions with ≥ 3 cm in the longest diameter: Yes vs No)
- Prior stem cell transplant (Yes vs No)
- Prior radiotherapy (Yes vs No)
- Ann Arbor stage III/IV (Yes vs No)
- Serum lactate dehydrogenase $>ULN$ (Yes vs No)
- Follicular Lymphoma Internal Prognosis Index (FLIPI-1 score)

7.5. Prior systemic anti-cancer therapy

For the FL patients in Phase 2a Cohort 1 and 2 and PTCL patients in Phase 2a Cohort 5 only, the number of prior regimens will be summarized numerically and categorically. Best overall response to the last regimen and time since the end of last regimen will be summarized descriptively. The therapies with the same regimen number are counted as one line of prior therapy.

In addition, the types of prior systemic anti-cancer regimens will be internally adjudicated and summarized for the FL patients in Phase 2a Cohort 1 and 2 and PTCL patients in Phase 2a Cohort 5.

Prior anti-cancer therapies for other subjects except FL subjects in Phase 2a Cohort 1 and 2 and PTCL patients in Phase 2a Cohort 5 will be listed only.

7.6. Medical History

Medical history will be coded using the Medical Dictionary for Regulatory Activities (MedDRA) (version 16.1 for Phase 1; version 21.1 for Phase 2a or higher). The number and percentage of subjects reporting a history of any medical condition, as recorded in the eCRF, will be summarized by system organ class (SOC) and preferred term (PT).

7.7. Prior and concomitant medications

Prior and concomitant medications will be coded using the World Health Organization (WHO) drug dictionary (version SEPTEMBER 2013 for Phase 1; version B2 Sep2018 for Phase 2a or higher) and further classified to the appropriate Anatomical Therapeutic Chemical (ATC) code.

Prior medications are defined as medications that started before the first dose date.

Concomitant medications are defined as medications that (1) started before the first dose of the study treatment and were continuing at the time of the first dose of the study treatment, or (2) were started on or after the first dose date of the study treatment up to 30 days after the last dose date.

The number and percentage of subjects reporting prior medication and concomitant medications will be summarized by ATC medication class level 2 and WHO drug preferred term.

